1.0 Study Summary

Study Title	Crowdsourcing an open COVID-19 chest radiograph imaging repository for artificial intelligence research
Study Design	Data repository.
Primary Objective	Assemble a crowdsourced, de-identified radiographic repository
Secondary Objective(s)	Train and validate existing COVID-NET deep learning diagnostic models
Research Intervention(s)/ Investigational Agent(s)	None
IND/IDE #	Not applicable.
Study Population	COVID-19 positive patients
Sample Size	1,000 positive cases, 10,000-20,000 total cases
Study Duration for individual participants	Participants will remain in the study for as long as they remain users of the web portal.
Study Specific Abbreviations/ Definitions	AWS: Amazon Web Services GCP: Google Cloud Platform AI: Artificial Intelligence DICOM: Digital Imaging and Communications in Medicine HL7 FHIR: Fast Healthcare Interoperability Resources CXR: Chest X-Ray COVID-19: Corona Virus Disease 2019

2.0 Objectives

- 2.1 The objectives of this project are to (1) assemble a crowdsourced, de-identified radiographic repository; and (2) train and validate existing COVID-NET deep learning diagnostic models.

3.0 Background

- 3.1 The COVID-19 pandemic is laying bare the need for accessible curated datasets that researchers can use to build clinical-grade artificial intelligence (AI) models. Researchers in China recently used deep learning models of clinical-grade AI trained on radiographic imaging at an exponential scale to detect COVID-19 cases and optimize allocation of limited resources. (Jin S, Wang B, Xu H, et al. Ai-assisted ct imaging analysis for covid-19 screening: Building and deploying a medical ai system in four weeks. medRxiv. 2020:2020.2003.2019.20039354. doi: 10.1101/2020.03.19.20039354). This research platform is currently not possible in the United States because there are no large accessible radiographic imagesets of COVID-19 patients to leverage. Therefore, the purpose of this project is to launch an interactive and HIPAA-compliant web portal—CovidImaging.com—where patients can securely share their radiographic imaging data. This portal will serve as an imaging repository for the purpose of training, testing, and validating an AI model aimed at earlier and more accurate disease detection in this global fight against COVID-19.

On January 30, 2020 the World Health Organization designated the COVID-19 outbreak that originated in Wuhan, China as a global health emergency. Since then, the virus has rapidly spread across the world as a pandemic, unfavorably affecting health care systems at the expense of primary healthcare requirements.¹ Symptomatic cases of COVID-19 present with clinical symptoms similar to viral pneumonia such as fever, shortness of breath, chills, fatigue, cough, and dyspnea that can progress to acute respiratory distress syndrome, requiring critical care and ventilation.² Bronchoalveolar lavage analysis and electron microscopy identified the causative agent to be a novel, positive-sense RNA virus in the Coronaviridae family, with spiked peplomers attached to its envelope.³ This family of viruses has also been associated with severe acute respiratory syndrome (SARS) and Middle East respiratory syndrome (MERS), which cause similar pneumonia-related mortality.

- 3.2 Preliminary reviews have been conducted to investigate the overlap of reported imaging features in SARS, MERS, and COVID-19 as it relates to onset of symptoms, progression of disease, and follow up. Early evidence suggests significant overlap in imaging features such as subpleural and peripheral areas of ground-glass opacity and consolidation, with initial chest imaging indicating abnormality in at least 85% of COVID-19 patients.⁴

In the absence of vaccines and specific therapeutic drugs for the prevention and treatment of COVID-19, detection of the disease plays a vital role in containment strategies that isolate infected people from the healthy population. Even though RT-PCR sensitivity for COVID-19 can be as low as 60-70%, it is currently the large-scale method of testing with its high specificity.⁷ The low sensitivity of RT-PCR, along with limitations of sample collection, time delay, transportation, and lab equipment, means that not enough COVID-19 positive people are being identified in time to prevent progressive infection of this highly contagious virus.

Given the respiratory involvement in COVID-19 infections, chest radiography has played an important role in screening, diagnosing, and developing treatment plans for patients with COVID-19-related pneumonia. Therefore, combining imaging with clinical and laboratory findings could facilitate the early diagnosis of COVID-19.⁵ Early detection would speed up treatment and allow for early patient isolation. This is essential for the implementation of public health surveillance, containment, and response for a highly communicable disease in which transmission can occur prior to onset of symptoms.⁶ Improving the precision of radiographic interpretation with AI models may improve detection rate and patient prognosis and thus help to reduce COVID-19 spread. As recently reported, chest CT demonstrates common radiographic features in almost all COVID-19 patients, including ground-glass opacities, multifocal patchy consolidation, and/or interstitial changes with a peripheral distribution.^{8,9}

Studies have also been conducted to compare the efficacy and diagnostic value of chest CT to RT-PCR tests in COVID-19 cases. A case report of 1014 patients in China concluded that chest CT has a high sensitivity for diagnosis of COVID-19, with 60% to 93% of cases showing initial positive CT diagnosis prior to the initial positive RT-PCR results.¹⁰ Another study with 51 patients having chest CT and RT-PCR assay within 3 days showed that the sensitivity of CT for

COVID-19 infection was 98%, compared to 71% RT-PCR sensitivity.¹¹ These studies further indicate the diagnostic value of chest radiographs alongside clinical and laboratory findings. This project will develop a large radiographic image repository which will be used to train and validate an AI deep learning model.

This project necessarily involves not only designing and refining a deep learning model, but also curating a repository of donated chest radiographs that will be used to train the novel model. Using a secure and HIPAA-complaint online platform, as has been designed for this project, will allow this project to employ a big data approach to improve the accuracy of the model. Since patients from healthcare facilities around the country will have equal opportunity to participate in the project, this portal will also provide an opportunity to expand the demographic pool in a way that previous studies could not.

4.0 Study Endpoints

4.1 N/A. This is not an interventional study.

5.0 Study Intervention/Investigational Agent

5.1 N/A. This is not an interventional study.

6.0 Procedures Involved

6.1 This study will develop the computational infrastructure to study human participants who have been screened for COVID-19 with chest radiographic imaging. We will develop a secure web app hosted at <https://CovidImaging.app> on Amazon Web Services (AWS) to collect and store PHI, and we have confirmed that UCF has existing business associate agreements in place with AWS to fulfill HIPAA regulations managing electronic PHI. We have implemented multi-factor authentication to track users of the web app. The first authentication is the RSA-encrypted password that the user must generate to use the web application. The second authentication is email verification. Beyond this two-factor authentication to establish an account, we will also track all IP addresses of all database transactions as a precaution.

When a patient first logs on to the web app, they will be prompted to sign a terms and conditions form through the application portal's DocuSign interface. Next, they will use a HIPAA-compliant DocuSign interface to sign informed consent and provide medical release for every site at which their imaging was performed.

The subjects will be asked to provide informed consent and to sign a medical release for their images for each clinical site where their

imaging was performed. Once we have received medical release, we will generate a Transfer Ticket associated with a unique TransferID that will track the DICOM transfer for the specific user and site. The TransferID is not considered PHI and is used to keep any PHI we collect on the web app separate from the images that are transferred. The web app provides an administrative dashboard for study coordinators to manage / flag TransferIDs for manual transfer or follow up. However, to ensure PHI is protected, TransferIDs are the only public identifier to reference images.

HIPAA mandates that the imaging sites to fulfill the patient's requests to release images in a timely fashion. If the site is new to us, Nautilus Medical will onboard a specific site coordinator who will oversee install of their Matrix Ray software that allows secure peer-to-peer DICOM image transfer. It is entirely conceivable that the site may not use the MatrixRay software and may send a standardized CD/DVD to us that we can import into our MatrixRay pipeline. Once the site is onboarded and / or the data is made available on MatrixRay, our web app will directly email the site coordinator to alert them that a new transfer is available for medical data release.

TransferID means that no PHI is ever transmitted by email as the site coordinator must log on to our web app to retrieve the patients' medical release for the DICOM transfer.

The site coordinator will then transfer the requested DICOM imaging through MatrixRay. Every DICOM transferred through MatrixRay is associated with the unique TransferID. Once that TransferID is received, we close the Transfer Ticket. Unfulfilled Transfer Tickets remain queued in an administrative interface for manual follow up by our team. Therefore, the only reason we collect PHI is to initiate the DICOM transfer process. The internal TransferID will track DICOM transfer process from medical release to DICOM receipt. PHI is only used to initiate DICOM transfer process through MatrixRay. Our study coordinators only track PHI internally through the TransferID of the admin panel.

Nautilus Medical provides their MatrixRay technology for peer to peer DICOM transfer as free for our academic use. There is no other relationship with the team and Nautilus. The technology is routinely used to exchange DICOM imaging for clinical purposes among different clinical sites. The two sites exchanging DICOM imaging must download a windows client that establishes a secure peer to peer connection to transfer the DICOM files. Nautilus facilitates onboarding of the sites initially to sign BAAs and establish a site coordinator. Nautilus does not record any PHI. Nautilus only makes the MatrixRay client for DICOM transfer and will onboard hospital

sites. Once a site is onboarded, the clinical providers will require a HIPAA compliant medical release form signed by the patient to transfer the imaging.

The app collects this medical release form which is also PHI. Our app communicates the patient name, date of birth, imaging site, and MRN (when available) to the clinical provider to initiate the transfer. The medical release form collects PHI that will only be shared to initiate DICOM transfer. The clinical site ultimately sends the requested DICOM files, and we will specifically ask for all radiographic imaging for each potential COVID case. The patient will need to provide name and site, and MRN is optional. PHI (i.e. patient name) may be embedded on the delivered DICOM files. This is likely if clinical providers have scanned film with PHI labels embedded in images. We should not assume the clinical providers will strip the DICOM files because when Nautilus onboards the clinical provider, they become a business associate that can transfer PHI. This is a potential source of PHI leak on AWS. To address concerns, our study coordinators (as listed on the IRB application) will curate every image transferred to ensure no such images with PHI embedded are released for machine learning. Coordinators will annotate out the PHI manually before the image is released. We will use standard de-identification scripts to strip the DICOM files delivered to us of any PHI and integrate only raw .tiff or .png into our AWS web application.

We will keep/save the de-identified DICOMs on AWS to a secure S3 location, and MatrixRay will only communicate PHI to this AWS S3. AWS will only serve to coordinate PHI that we collect from the patient in EC2 instance independent from the S3 for imaging. EC2 serves to host our web applications and integrate imaging through transfer IDs. Once we receive their DICOM imaging, our app has a DICOM viewer that the patient can use to see their images. We will use MatrixRay on AWS to de-identify DICOM files by extracting images for machine learning. Only researchers and study coordinators approved by the IRB will curate de-identified images into labeled research imagesets that we will use for machine learning. PHI is not important to machine learning, so as a rule, we will keep all PHI we collect on AWS separate from any machine learning instances that will be either local at UCF or on Microsoft or Google clouds thereby protecting against any PHI leak.

To maintain the separation of images from PHI, the web interface never shows explicit PHI (such as the patient name or MRN) on the same screen as an Image which further reduces the leak of PHI tied to images by screen shots or other untoward attempt.

Within our AWS app, we have embedded a UCF-managed Qualtrics backend to issue interactive surveys within our web app. We have developed an initial COVID-19 questionnaire to learn

clinical outcomes to predict from de-identified imaging. Future surveys will be issued once IRB-approved as we grow our app-based community. These surveys may be interactive and will allow for a platform where researchers can longitudinally follow patients through the rapidly evolving pandemic. By keeping this Qualtrics backend managed by UCF, we also minimize any PHI leaks.

As we develop AI models, we will publish de-identified labeled imagesets on Zenodo, which issues digital object identifiers (DOI) that can be cited in our research, with tight integration with GitHub to store de-identified image assets. We may issue imagesets for machine learning based on clinical outcomes or other features learned from patient surveys. Once de-identified assets are registered on Zenodo/GitHub, they will be maintained as open and accessible pending funding. We have at least three years of funding from [name] startup to maintain this repository, and we will be seeking NIH grants to develop the resource for the AI community in perpetuity.

The process can be outlined as follows:

1. Patient visit the informational covidimaging.com which directs them to sign up for app at covidimaging.app
 - a. Patient signs informed consent on DocuSign via app
 - b. App collects patient's full name and date of birth
 - c. App collects and validates patient's email address
2. Patient fills questionnaires about his/her imaging
 - a. App collects name, date of birth, site of imaging, medical record number, and date of imaging if available
 - b. Opens a new Transfer Ticket that serves to de-couple the PHI collected on the app from the imaging transferred
3. Patients fill out questionnaires about their COVID-19 course via app
 - a. Questionnaire asks about patient's clinical course, including molecular diagnosis of infection and convalescence
4. Web app sends email to the imaging site initiate DICOM transfer
 - a. No PHI is sent via email, just a notification that a new Transfer Ticket was created
 - b. If known site, app emails the Transfer Ticket to the site coordinator
 - c. If unknown site, app emails the Transfer Ticket to the Nautilus coordinator
 - i. Nautilus onboards site to use MatrixRay
 - ii. Nautilus emails the Transfer Ticket to site coordinator
5. Site coordinator transfers DICOM through MatrixRay to web app
6. Web app closes Transfer Ticket
7. Research team assembles de-identified imagesets for machine learning to Zenodo to issue digital object identifiers (DOI) with GitHub integration to store de-identified images. If applicable, the research team de-identifies images with PHI

8. Research team uses repository to train, test, and validate the open COVID-NET model on Microsoft, Google, or Amazon AI platforms to predict CXR outcomes.

[figure not shown]

Figure: CovidImaging Data Flow diagram. Patients log on to the web app to sign informed consent and provide a medical release for each site they have had imaging. PHI data flows from patients on WWW network through the web interface hosted on AWS network. Coordinators at remote imaging sites are alerted to login to the web app and send imaging through MatrixRay to our AWS servers. Standard DICOM de-identification scripts on the MatrixRay receiving client will only save de-identified DICOMS to a secure S3 location. We will use a Qualtrics back end to issue surveys to participants about the clinical course of their disease. Study coordinators will be able to curate these images to publish de-identified, labeled imagesets on Zenodo with tight GitHub integration. AI platforms (such as Google Cloud and Microsoft Azure) will only access the de-identified imagesets to develop models for training, testing, and validating COVID-19 radiology models.

6.2

The only foreseeable risks posed to the study participants is the risk of exposure of their protected health information. To prevent this, all radiographic images will be de-identified and all patient information will be encoded as detailed above in this protocol.

6.3

We rely on AWS best practice workloads for securing patient data collected on the web app within the scope of the U.S. Health Insurance Portability and Accountability Act (HIPAA). All data collected is stored and encrypted behind password authentication. No PHI is ever exposed to an open network. When new imaging sites are onboarded, study coordinators at those sites are emailed.

6.4 We will collect the data through a survey questionnaire hosted on UCF's Qualtrics.

https://ucf.qualtrics.com/jfe/form/SV_9pdRxnqiKFvhsrP

- There are no plans for long-term follow-up data collection (once all research related procedures are complete).

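### Protocol 6.1 calls the TransferID both public and internal, although imaging sites hold it beside the patient's name; released images need a separate code

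*Protocol*

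**What the plan says.** All of the following is in Protocol Section 6.0 unless another section is named.

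- **Creation.** After the patient signs a release, "we will generate a Transfer Ticket associated with a unique TransferID that will track the DICOM transfer for the specific user and site". The code is declared not to be PHI.
- **Attachment to images.** "Every DICOM transferred through MatrixRay is associated with the unique TransferID".
- **Status, first statement.** "However, to ensure PHI is protected, TransferIDs are the only public identifier to reference images".
- **Status, second statement.** "The internal TransferID will track DICOM transfer process from medical release to DICOM receipt".
- **Who receives it.** Step 4b: "If known site, app emails the Transfer Ticket to the site coordinator". Under step 4c, for a site not yet known, the ticket goes to the Nautilus coordinator, who forwards it to the site. Step 4a describes the email as a bare notification without PHI.
- **Where the name comes in.** The protocol explains that "no PHI is ever transmitted by email as the site coordinator must log on to our web app" to obtain the signed release. The app also gives the provider the patient's name, date of birth, imaging site and, when available, record number.
- **Release.** Labelled imagesets are published on Zenodo with GitHub storage. On the labels: "We may issue imagesets for machine learning based on clinical outcomes or other features learned from patient surveys".

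Section 17.3 defines a separate subject number (C19AI001 onward) and Section 17.2 commits to Safe Harbor de-identification. Neither says which code the released files carry.

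**The concern.** One code is given two jobs that do not fit together. As a working key it must be known to the imaging site, which has to match a request to a named patient in order to send the right images. As a public key it is supposed to protect privacy by standing in for the patient. A code that an outside party holds beside a name cannot do the second job with respect to that party.

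Section 6.2 names exposure of protected health information as the only foreseeable risk to participants, and the recruitment text in Section 13.0 promises prompt de-identification. The information at stake is mainly the label. The site already has the image and the identity, but it does not necessarily have the patient's own survey answers on clinical course and outcome. A shared code would turn linking those answers to a name into a simple lookup.

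**Working it through.** The plan gives no figure on this point and no arithmetic applies. The check follows the TransferID from creation to release and asks at each link whether the protocol states it, implies it or leaves it open.

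| Link | Where | Finding |
|---|---|---|
| 1. The code is unique to one user and one site | 6.1, creation of the ticket | Stated |
| 2. Each transferred DICOM is tied to the code | 6.1, MatrixRay transfer | Stated |
| 3. The imaging site receives the ticket | 6.1, steps 4b and 4c | Stated, although step 4a calls the email only a notification |
| 4. The imaging site can pair the code with a name | 6.1, log-on to retrieve the release; app sends name, date of birth, record number | Follows from the text: the site must match ticket to patient to make the transfer |
| 5. Nautilus can pair the code with a name | 6.1, description of Nautilus | Not supported: it gets the ticket only for unknown sites and is said to record no PHI |
| 6. The code is public | 6.1, two statements | Contradictory: public in one, internal in the other |
| 7. Released Zenodo/GitHub files carry the code | 6.1, 7.3, 17.3 | Not stated; the natural reading of the public-identifier sentence |
| 8. Released files carry survey-derived labels | 6.1 | Stated as a possibility |

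Links 1 to 4 establish that the sending site holds name and TransferID together. Link 6 is a conflict on the face of the text, whatever was intended. Link 7 decides whether the conflict has a consequence.

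Two considerations favour the reading that released files carry the code. First, a public identifier for images has little purpose if no public image uses it. Second, Section 14.3 promises to delete a withdrawing subject's images from GitHub and Zenodo, which requires some key from subject to published file. The TransferID is the only key that the protocol expressly assigns to images.

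If link 7 holds, the route is short: a site takes the TransferID from its own transfer record, finds it in the open set, and reads the label. If link 7 does not hold, no such lookup exists and what remains is the contradiction between the two statements.

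**The case against.** The best defence is that the sentence sits in a paragraph about managing transfers, directly after the description of the coordinators' dashboard. Public could there mean visible outside the PHI store while the transfer is under way, and the later statement describes a code whose work runs only as far as receipt of the images. Section 17.3 supplies another candidate identifier, and the public handle that 6.1 names for a released imageset is a DOI. This stands as far as it goes: that released files carry the TransferID is an inference. It does not remove the contradiction. Section 17.3 does not assign its subject numbers to images or releases, and a DOI identifies a dataset, not one image within it.

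A second objection is that the site already has the original image and could find its patient in the open set by comparing images, with no code at all. This also stands. It limits what any change of code can achieve, but comparing images is a different effort from looking up a shared key.

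A reader might infer more than the protocol supports:

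- **That Nautilus could identify patients.** The protocol says it records no PHI, and it sees the ticket only for sites not yet onboarded.
- **That anyone with access to the site's mailbox could identify patients.** The email carries no PHI, and the signed release is reached only by logging on.
- **That release is irreversible.** Section 14.3 provides for deletion from both public hosts. Copies already downloaded would be out of its reach, but the hosted files would not.

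**Conclusion.** The point holds in a limited form. Section 6.1 contradicts itself on whether the TransferID is public or internal. Because imaging sites hold that code with the patient's identity, the public version of the rule weakens protection against the one foreseeable risk that Section 6.2 names.

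The size cannot be fixed from the protocol. If released files carry the TransferID, every released image is open to lookup by the site that sent it; if they do not, none is. A reader might take the planned 10,000 to 20,000 cases in Section 7.1 as the number exposed. That figure is the planned collection, not a count of released images keyed by TransferID, and it should not be used that way.

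The conclusion rests on two assumptions: that the site keeps, or can retrieve, the TransferID next to the patient's record, which the transfer procedure makes close to unavoidable; and, for any actual exposure, that the public-identifier sentence governs the Zenodo and GitHub files. Disclosure of new information further requires that the release carry survey-derived labels, which the protocol allows but does not commit to.

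**What to change.** Reconcile the two statements in Section 6.1 by replacing the public-identifier sentence with text such as:

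> TransferIDs are internal and are never published. Each released image and subject receives a new random code unrelated to the TransferID. The crosswalk is kept only on AWS, restricted to IRB-listed staff, and is used to carry out the deletions promised in 14.3.

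The change should be made before the first imageset is released, since copies downloaded before a correction could not be recalled.

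The cost is one replaced passage and one crosswalk table to maintain; no new data or participants are needed. The crosswalk keeps the withdrawal promise workable. The limit should be acknowledged: a new code removes the lookup, but it does not prevent a site from recognising images it already holds.
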